6.0 STRATIFICATION FACTORS

Balancing on patient characteristics will not be necessary due to the large sample size. Thus, stratification factors are not applicable to this study.

7.1 Good Medical Practice

The following pre-study tests should be obtained within 28 days prior to registration in accordance with good medical practice. Results of these tests do not determine eligibility and minor deviations would be acceptable if they do not impact on patient safety in the clinical judgment of the treating physician. The Study Coordinator must be contacted if there are significant deviations in the values of these tests.

- a. Chest x-ray that is negative for metastatic disease. If a chest x-ray was done as part of the original diagnostic and/or preoperative workup and was negative, it does not need to be repeated.
- b. CBC (WBC $\geq 3,000/\mu I$, ANC $\geq 1,000/\mu I$, platelets $\geq 100,000/\mu I$).
- c. Total bilirubin that is ≤ 2 x the institutional upper limit of normal and SGOT or SGPT that is ≤ 3 x the institutional upper limit of normal.
- d. Calcium, albumin, magnesium and phosphate within institutional normal limits.
- e. Electrolytes (sodium, potassium, chloride, bicarbonate)
- f. Alkaline phosphatase within institutional normal limits.
- g. Ultrasound or CT scan of the abdomen if liver function tests (alkaline phosphatase, bilirubin, SGOT or SGPT) are elevated without a clear cause.
- h. CT scan of the chest and abdomen and a bone scan are recommended in patients at high risk for harboring metastatic disease, such as patients with Stage III disease or those with 10 or more lymph nodes involved by malignancy. The combination of chest x-ray, liver ultrasound and bone scan (with CTs only for abnormal chest x-ray or ultrasound) will also be considered acceptable in these high risk patients.

7.2 Pre-Treatment Guidelines

Patients will be randomized to zoledronic acid (Arm 1) or to clodronate (Arm 2) or to ibandronate (Arm 3). The duration of bisphosphonate therapy is 3 years. After three years, patients may receive non-protocol therapy at the physician's discretion.

Investigators are encouraged to begin bisphosphonate therapy as soon as possible after surgery. Patients may be registered and begin bisphosphonate therapy prior to, simultaneously, or after systemic therapy. Patients receiving hormonal therapy alone (no chemotherapy) or pre-operative chemotherapy should be enrolled within 84 days (12 weeks) after the date of final surgical procedure. Patients receiving adjuvant post-operative chemotherapy may be enrolled up to 8 weeks after completion of chemotherapy (see Section 5.3).

Women of child-bearing potential must have a pregnancy test performed within 72 hours prior to initiation of treatment.

7.3 Treatment Schedule

For patients receiving zoledronic acid, peripheral or central intravenous access may be used. During the first 6 months of dosing, zoledronic acid should be administered to patients in Arm 1 monthly (i.e. if treatment begins on the 1st of the month, then the subsequent doses are given on the 1st of each month thereafter), however minor deviances from this dosing interval are acceptable. It is suggested that the infusions be given within \pm 2 days (2 days earlier or later). During the remaining period of dosing, zoledronic acid may be given within \pm 1 week (7 days earlier or later). The last dose of zoledronic acid in Arm 1 should be administered at Month 33. Oral bisphosphonates given in Arms 2 and 3 are to continue daily until the first day of Month 36 and are then discontinued.

NOTE: For Arm 1, monthly dosing of zoledronic acid is given for 6 doses, q 3 monthly dosing is given for 9 doses.

DRUG	DOSE	RX ROUTE	DAY	INTERVAL
Arm 1 Zoledronic acid	*4 mg	IV over 15 minutes	1	q monthly x 6 months then q 3 months for 2.5 years
Arm 2 Clodronate	1,600 mg	PO	1	q day x 35 months
Arm 3 Ibandronate	50 mg	РО	1	q day x 35 months

^{*} Upon treatment initiation, the recommended zoledronic acid doses for patients with reduced renal function (mild and moderate renal impairment) are listed below. These doses are calculated to achieve the same AUC as that achieved in patients with creatinine clearance of 75 ml/min. Creatinine clearance (CrCl) is calculated using the Cockcroft-Gault formula:

(140-age) x wt (kg x 0.85 (if female) 72 x creatinine (mg/dL)

Baseline Creatinine Clearance (ml/min)	Zoledronic Acid recommended dose. (Calculated assuming AUC of 0.66 mg/hr/L) (CrCl = 75 ml/min)
> 60	4 mg
50 - 60	3.5 mg
40 - 49	3.3 mg
30 - 39	3 mg

7.4 Dental Examination

Patients will undergo a dental exam within 6 months prior to initiation of treatment. The Dental Examination Form (Form #30100) should be completed by a dental health professional (may be retrospectively completed if the exam was prior to initiation of treatment). The exam should include visual inspection and periodontal probing. Specifically, evaluation of risk factors for osteonecrosis of the jaw should be evaluated. X-rays are not required, but should be performed, if indicated to assess degree of periodontal involvement and endodontic (root canal) problems.

Patients on chemotherapy, who have the potential to develop neutropenia, should avoid undergoing teeth cleaning or elective restorative procedures due to possible increased risk of infection. Patients are expected to undergo standard dental examinations and care while on study. Financial assistance will be available for baseline dental exams for patients with severe financial need and without dental insurance who would not have access to dental care by any other means. Contact the Southwest Oncology Group Operations Office at [name] for further information. X-rays are not required by this study and will not be covered unless significant baseline problems are identified.

- 7.5 Patients may receive radiation therapy to breast/chest wall/lymph node groups while on protocol treatment at the treating physician's discretion.
- 7.6 Patients should have supplemental administration of oral calcium and vitamin D. Recommended dose of calcium for premenopausal women is 1,000 mg PO daily, and range for postmenopausal women is 1,200-1,500 mg PO daily. The recommended daily dose of vitamin D is 400-800 units/day. These supplements should not be taken within 30 minutes of oral bisphosphonates.
- 7.7 Oral bisphosphonates should be taken at least one hour before the first food or drink of the day other than water. To facilitate delivery to the stomach, oral bisphosphonates should be swallowed while the patient is in an upright position and with a full glass of plain water (6 to 8 oz). Patients should not lie down for 30 minutes after taking the medication.

Calcium supplements and calcium-, aluminum-, and magnesium-containing medications may interfere with the absorption of oral bisphosphonates and should be taken at a different time of the day.

7.8 Pill Compliance: Patients are encouraged to keep their own pill diary and should bring the diary with them to each follow-up visit. Diaries will not be collected, but any missed pills during the last month of treatment should be reported on the \$0307 Treatment Summary Form (Form #31453).

7.9 Treatment Evaluations

Physical exams and labs (including CBC, electrolytes, calcium, phosphate, magnesium, albumin, and LFTs) should be performed prior to dosing (ideally Day 1) of Month 2, 4, 6, then q 3 months until Month 36.

For Arm 1, serum creatinine testing must be performed within 7 days prior to administering subsequent zoledronic acid dosing q monthly for Months 2-6, then q 3 months until Month 36.

For Arms 2 & 3, serum creatinine testing should be performed ± 7 days (7 days earlier or later) q monthly for Months 2-6, then q 3 months until Month 36.

7.10 End of Treatment Evaluation

An end of treatment physical examination and a bone scan will be obtained in all patients at the end of protocol treatment, on Day 1 of Month 36 or up to 14 days after Day 1 of Month 36. Patients who have had a bone scan within 6 months prior to ending treatment will not be required to have the scan repeated. Additionally, a dental examination will also be required at the end of protocol treatment (within 6 months after study completion or removal from protocol treatment, see Section 7.11). The end of treatment dental examination must be performed regardless of how long the patient was on treatment (including one month or less). For patients without insurance to cover these examinations, financial assistance will be available. Contact the Southwest Oncology Group Operations Office at [name] for further information.

7.11 Evaluation at the time of recurrence

a. Recurrence of disease must be adequately demonstrated. Suspected recurrence should be biopsied or otherwise confirmed if at all possible. Good medical practice requires biopsy proof of recurrent disease, as such documentation helps avoid the occasional mistake of misidentification of a benign lesion as recurrence or of second primary cancers as recurrence. If biopsy proof of recurrence cannot be obtained, radiologic diagnosis will be allowed at the discretion of the treating physician.

- b. Patients must be restaged at the time of recurrence. All patients with recurrence must have the following studies within 30 days of diagnosis and/or biopsy documentation of recurrence.
 - 1. Nucleotide bone scan, CT of chest and abdomen (MRI, CAT or ultrasound of the liver may be substituted for abdomen CT if desired).
 - 2. For patients experiencing bone pain with other sites of recurrence, plain films will be obtained on the painful sites if the bone scan is negative.
 - 3. For patients with other possibly tumor related symptoms, appropriate radiologic or other studies should be obtained to document the sites of disease.

7.12 Criteria for Removal from Protocol Treatment:

- a. Invasive recurrence of disease or diagnosis of new invasive breast primary. A new diagnosis of ipsilateral or contralateral DCIS without an invasive component is not considered to be a recurrence or a second primary.
- b. Unacceptable toxicity (see Section 8.0).
- c. Greater than 3 months in delay of protocol treatment.
- d. Completion of three years of protocol treatment.
- e. The patient may withdraw from the study at any time for any reason.
- 7.13 All reasons for discontinuation of treatment must be documented on the Off-Treatment Notice.
- 7.14 All patients will be followed until death or for 10 years, whichever is first.

8.0 TOXICITIES TO BE MONITORED AND DOSAGE DELAY AND MODIFICATIONS

- 8.1 Two different versions of the NCI Common Terminology Criteria for Adverse Events (CTCAE) will be used on this study.
 - a. Serious Adverse Event (SAE) reporting

The CTCAE (NCI Common Terminology Criteria for Adverse Events) Version 4.0 will be utilized **for SAE reporting only**. The CTCAE Version 4.0 is identified and located at the CTEP website at http://ctep.cancer.gov/protocolDevelopment/electronic applications/ctc.htm. All appropriate treatment areas should have access to a copy of the CTCAE Version 4.0.

b. Routine toxicity reporting

This study will utilize the CTCAE Version 3.0 for routine toxicity reporting. A copy of the CTCAE Version 3.0 can be downloaded from the CTEP home page (http://ctep.cancer.gov). All appropriate treatment areas should have access to a copy of the CTCAE Version 3.0.

- 8.2 Bisphosphonate therapy must be held for any Grade 3 or greater toxicity (that is attributed to the bisphosphonate by the treating physician). If toxicity has not resolved within 3 months, then the patient must be removed from protocol treatment. If toxicity resolves (Grade 0-1) within 3 months, the protocol treatment should be restarted. If Grade 3 or greater toxicity reoccurs, then the patient must be removed from protocol treatment.
- 8.3 Renal Toxicity: For any increase of 0.5 mg/dL from normal baseline creatinine that is > IULN, or any increase of ≥ 1 mg/dL from an abnormal baseline creatinine that is > IULN, bisphosphonate therapy should be held, and serum creatinine must be monitored until it returns to within 10% of baseline. Once creatinine returns to within 10% of baseline, bisphosphonate therapy can be reinitiated at the same dose prior to treatment interruption.

\$0307 Page 31a Revised 7/13/09 Revised 8/30/10 Revised 4/21/11 Revised 3/28/14

For patients in the zoledronic acid arm with an increased creatinine, consider increasing the infusion duration to 30 minutes in subsequent cycles.

Grade 3 or higher creatinine elevations (> 3 x the institutional upper limit of normal) that is attributed to the bisphosphonate by the treating physician will require removal of the patient from protocol treatment.

- 8.4 Bisphosphonates from any of the 3 arms may be held or delayed for up to 3 months for any reason without requiring removal from protocol treatment. The total duration of treatment will be 35 months (through Day 1 of Month 36) for the clodronate and ibandronate arms regardless of how many doses may have been missed during this period. The last dose on the zoledronic acid arm should be administered at Month 33, but no later than 36 months after registration due to treatment delays. If treatment is delayed for more than one week during the first 6 months of treatment on zoledronic acid, the schedule should be adjusted so that there is at least 3 weeks between successive doses, until all 6 monthly doses have been given, after which every 3 months dosing can begin. Otherwise, the original schedule on the zoledronic acid arm should be adhered to following treatment delays.
- 8.5 Osteonecrosis of the jaw: Completion of the Osteonecrosis Jaw Lesion Form (Form #52641) will be required for any patient diagnosed with osteonecrosis of the jaw. Because of the long half-life of bisphosphonates in bone, it is not clear that stopping the bisphosphonate therapy will aid in healing. Consultation with the **S0307** Jaw/Dental Health Coordinator, [name] ([name]), is recommended in this situation.
- 8.6 For treatment or dose modification related questions, please contact [name] at [name] or [name] at [name] or [name], BSN at [name] (e-mail: [contact]).
- 8.7 Toxicities (including suspected reactions) that meet the expedited reporting criteria as outlined in Section 16.0 of the protocol must be reported to the Operations Office, Study Coordinator and the NCI via CTEP-AERS, and to the IRB per local IRB requirements.

| | _ | | | | |
 |
 |
 |
 | |
 | | | | | Treatment | f |
|-------|---------------------------------------|-------|-------|---|---
--

--
--
--
--
--|---|---
--|---|---|---|--------|
| PRE | Month | Month | Month | Month | Month | Month
 | Month
 | Month
 | Month
 | Month | Month
 | Month | Month | Month | Month | Month | Follow |
| STUDY | 1 | 2 | 3 | 4 | 5 | 6
 | 9
 | 12
 | 15
 | 18 | 21
 | 24 | 27 | 30 | 33 | 36 | Up |
| | | | | | |
 |
 |
 |
 | |
 | | | | | | |
| Χ | | X | | Х | | Х
 | Х
 | Х
 | Х
 | Х | Х
 | Х | Х | Х | X | Χ | Χ |
| Χ | | X | | Х | | Х
 | Х
 | X
 | X
 | Х | X
 | Х | Х | Х | X | Χ | Χ |
| Χ | | | | | | Х
 |
 | Х
 |
 | Х |
 | Х | | Х | | Χ | Χ |
| | | X | | X | | Х
 | X
 | Х
 | Х
 | X | Х
 | Х | Х | Х | Х | Χ | |
| Χ | | | | | |
 |
 |
 |
 | |
 | | | | | Х | |
| | | | | | |
 |
 |
 |
 | |
 | | | | | | |
| Х | | Χ | | Χ | | Χ
 | Χ
 | Χ
 | Χ
 | Χ | Χ
 | Х | Х | Х | Χ | X | |
| Х | | Х | | х | | Х
 | Х
 | Х
 | Х
 | х | Х
 | х | х | Х | Х | Х | |
| Х | | Х | | Х | | Х
 | Х
 | Х
 | Х
 | Х | Х
 | Х | Х | Х | Х | Х | |
| Χ | | X | | Х | | Х
 | Х
 | X
 | X
 | Х | X
 | Х | Х | Х | X | Χ | |
| Χ | | X | X | Х | Х | Х
 | Х
 | X
 | X
 | Х | X
 | Х | Х | Х | X | Χ | |
| Χ | | | | | |
 |
 |
 |
 | |
 | | | | | | |
| Χ | | | | | |
 |
 |
 |
 | |
 | | | | | | |
| | | | | | |
 |
 |
 |
 | |
 | | | | | | |
| Χ | | | | | |
 |
 |
 |
 | |
 | | | | | | |
| X† | | | | | |
 |
 |
 |
 | |
 | | | | | Χδ | |
| X† | | | | | |
 |
 |
 |
 | |
 | | | | | | |
| | | | | | |
 |
 |
 |
 | |
 | | | | | | |
| Χ | | | | | |
 |
 |
 |
 | |
 | | | | | | |
| Χ | | | | | |
 |
 |
 |
 | |
 | | | | | | |
| Х | | | | | |
 |
 |
 |
 | |
 | | | | | | |
| | | | | | |
 |
 |
 |
 | |
 | | | | | | |
| | Х | Х | Х | Х | Х | Χ
 | Χ
 | Х
 | Х
 | Х | Х
 | Х | Х | Х | Х | | |
| | X | X | X | X | X | X
 | X
 | X
 | X
 | X | X
 | X | X | X | X | | |
| | X | X | X | X | X | X
 | X
 | X
 | X
 | X | X
 | X | X | X | X | | |
| | X X X X X X X X X X X X X X X X X X X | X | STUDY | STUDY 1 2 3 X X X X X X X X X X X X X X X X X X X X X X X X X X X X X X X X X X X X X X X X X X X X X X X X X X X X X X | STUDY 1 2 3 4 X X X X X X X X X X X X X X X X X X X X X X X X X X X X X X X X X X X X X X X X X X X X X X X X X X X X X X X X X X X X X X X X | STUDY 1 2 3 4 5 X X X X <tr< td="">STUDY 1 2 3 4 5 6 X X X X X X X X X X X X X X X X X X X X X X X X X X X X X X X X X X X X X X X X X X X X X X X X X X X X X X X X X X X X X X X X X X X X X X X X X X X X X X X X X X X X X X X XSTUDY 1 2 3 4 5 6 9 XSTUDY 1 2 3 4 5 6 9 12 XSTUDY 1 2 3 4 5 6 9 12 15 X<!--STUDY 1 2 3 4 5 6 9 12 15 18 X<	STUDY 1 2 3 4 5 6 9 12 15 18 21 X	STUDY 1 2 3 4 5 6 9 12 15 18 21 24 X	STUDY 1 2 3 4 5 6 9 12 15 18 21 24 27 X X X X X X X X X X X X X X X X X
 X <td< td="">STUDY 1 2 3 4 5 6 9 12 15 18 21 24 27 30 X <t< td="">STUDY 1 2 3 4 5 6 9 12 15 18 21 24 27 30 33 X <	 PRE	</t<>	</td<>					</tr<> | STUDY 1 2 3 4 5 6 X X X X X X X X X X X X X X X X X X X X X X X X X X X X X X X X X X X X X X X X X X X X X X X X X X X X X X X X X X X X X X X X X X X X X X X X X X X X X X X X X X X X X X X X STUDY 1 2 3 4 5 6 9 XSTUDY 1 2 3 4 5 6 9 12 XSTUDY 1 2 3 4 5 6 9 12 15 X<!--STUDY 1 2 3 4 5 6 9 12 15 18 X<	STUDY 1 2 3 4 5 6 9 12 15 18 21 X	STUDY 1 2 3 4 5 6 9 12 15 18 21 24 X
 X X	STUDY 1 2 3 4 5 6 9 12 15 18 21 24 27 X <td< td="">STUDY 1 2 3 4 5 6 9 12 15 18 21 24 27 30 X <t< td="">STUDY 1 2 3 4 5 6 9 12 15 18 21 24 27 30 33 X <	 PRE	</t<>	</td<>				| STUDY 1 2 3 4 5 6 9 X STUDY 1 2 3 4 5 6 9 12 XSTUDY 1 2 3 4 5 6 9 12 15 X<!--STUDY 1 2 3 4 5 6 9 12 15 18 X<	STUDY 1 2 3 4 5 6 9 12 15 18 21 X	STUDY 1 2 3 4 5 6 9 12 15 18 21 24 X
 X X X	STUDY 1 2 3 4 5 6 9 12 15 18 21 24 27 X <td< td="">STUDY 1 2 3 4 5 6 9 12 15 18 21 24 27 30 X <t< td="">STUDY 1 2 3 4 5 6 9 12 15 18 21 24 27 30 33 X <	 PRE	</t<>	</td<>			| STUDY 1 2 3 4 5 6 9 12 X STUDY 1 2 3 4 5 6 9 12 15 X<!--STUDY 1 2 3 4 5 6 9 12 15 18 X<	STUDY 1 2 3 4 5 6 9 12 15 18 21 X	STUDY 1 2 3 4 5 6 9 12 15 18 21 24 X	STUDY 1 2 3 4 5 6 9 12 15 18 21 24 27 X <td< td="">STUDY 1 2 3 4 5 6 9 12 15 18 21 24 27 30 X X X X X X X X X X X
X <t< td="">STUDY 1 2 3 4 5 6 9 12 15 18 21 24 27 30 33 X <	 PRE	</t<>	</td<>		| STUDY 1 2 3 4 5 6 9 12 15 X </td STUDY 1 2 3 4 5 6 9 12 15 18 X<	STUDY 1 2 3 4 5 6 9 12 15 18 21 X	STUDY 1 2 3 4 5 6 9 12 15 18 21 24 X	STUDY 1 2 3 4 5 6 9 12 15 18 21 24 27 X <td< td="">STUDY 1 2 3 4 5 6 9 12 15 18 21 24 27 30 X <t< td="">STUDY 1 2 3 4 5 6 9 12 15 18 21 24 27 30 33 X <	 PRE	</t<>	</td<>	| STUDY 1 2 3 4 5 6 9 12 15 18 X
X X< | STUDY 1 2 3 4 5 6 9 12 15 18 21 X | STUDY 1 2 3 4 5 6 9 12 15 18 21 24 X | STUDY 1 2 3 4 5 6 9 12 15 18 21 24 27 X <td< td="">STUDY 1 2 3 4 5 6 9 12 15 18 21 24 27 30 X <t< td="">STUDY 1 2 3 4 5 6 9 12 15 18 21 24 27 30 33 X <	 PRE	</t<>	</td<> | STUDY 1 2 3 4 5 6 9 12 15 18 21 24 27 30 X <t< td="">STUDY 1 2 3 4 5 6 9 12 15 18 21 24 27 30 33 X <	 PRE	</t<> | STUDY 1 2 3 4 5 6 9 12 15 18 21 24 27 30 33 X < | PRE |

NOTE: Forms are found in Section 18.0. Forms submission guidelines may be found in Section 14.0.

- @ Patient height should also be assessed at prestudy.
- § Results of these tests do not determine eligibility but are suggested at prestudy for Good Medical Practice (see Section 7.1). These tests are required during treatment as scheduled to assess toxicity.
- * Albumin is needed only if a serum calcium is drawn. It is not needed for an ionized calcium.
- π Liver function tests: SGOT or SGPT, Bilirubin, and Alkaline Phosphatase
- Ω Arm 1: Zoledronic Acid will be administered by IV on Day 1 q monthly for the first 6 months, however minor deviations are acceptable. It is suggested that the infusions be given within
 - ± 2 days. During the remaining period of dosing, zoledronic acid may be given within ± 1 week (7 days earlier or later). NOTE: Monthly dosing of zoledronic acid is given for 6 doses, q 3 monthly dosing is given for 9 doses (see Section 7.3 for definition of monthly).
- ψ Arm 2: Clodronate will be given PO q day . Discontinue on the first day of Month 36.
- α Arm 3: **Ibandronate** will be given PO q day. Discontinue on the first day of Month 36.
- £ Bone scan should be done at baseline if the patient has bone pain (see Section 5.10), after 3 years of study drug treatment, or when the patient goes off study if it is prior to 3 years. Patients who have had a bone scan within six months of ending treatment will not be required to have the scan repeated.
- β It is strongly recommended that patients already registered to the protocol at the time of Amendment #3 be given the oppportunity to consent to submission of whole blood specimen prior to their next blood draw for routine laboratory testing. The whole blood specimen may be drawn at any time during the patient's clinical care or planned phiebotomy and at any time during study participation or follow-up. Patients need not be on protocol treatment at the time of this draw.
- † CT scan of the chest and abdomen and bone scan are recommended for some patients at prestudy according to Good Medical Practice as outlined in Section 7.1f,g.
- f All patients including patients off protocol treatment prior to recurrence should return for disease assessments at least every 6 months for 5 years and then annually for 5 years or until death (whichever occurs first). See Section 7.11 for restaging at recurrence.
- λ Dental exam should be performed at the beginning and end of the treatment (regardless of how long the patient was on protocol treatment, see Section 7.10). Complete the Dental Examination Form (Form# 30100). To keep in line with patient's normal dental exam schedule, exams 6 months pre-enrollment and 6 months post-completion of study (or removal from protocol treatment, see Section 7.12) are required.
- Arm 1: To be performed within 7 days prior to registration, and within 7 days prior to administering all subsequent doses.
 Arm 2/Arm 3: To be performed within 7 days prior to registration and within ± 7 days (7 days earlier or later) of q monthly for Months 2-6 and q 3 month patient visits.
- $\Delta\,$ To be performed within 72 hours prior to initiation of treatment.
- € All end of treatment-evaluations occur on Day 1 of Month 36, or up to 14 days after Day 1 of Month 36.
- δ Only a bone scan is acceptable at End of Treatment (see Section 7.10)

\$0307 Page 32 Revised 6/12/06 Revised 9/25/06 Revised 1/25/07 Amended 6/18/07 Amended 3/11/08 Revised 7/13/09 Revised 1/21/10 Revised 4/21/11 Revised 10/11/11

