 - a. Drug Accountability: The principal investigator, or authorized designee, must maintain careful record of the receipt, disposition, and return of all zoledronic acid using the NCI Investigational Drug Accountability Record Form available on the CTEP forms page http://ctep.cancer.gov/forms/. Institution specific electronic logs allowable if approved by NCI.
 - b. Drug Returns: All unused drug supplies should be returned to Novartis Pharmaceutical for destruction. Returned drug must be sent with the zoledronic acid return form, which can be requested by contacting Novartis Pharmaceuticals. The Novartis contact information can be found on the \$0307 abstract page of the SWOG website (www.swog.org).
- 3.2 Clodronate (Bonefos®) (NSC-713466) (IND-71,481)
 - DESCRIPTION

Clodronate (Bonefos®) is not FDA-approved for use in the U.S.

Manufacturer: Bayer Schering Pharma Oy, [name].

Active Ingredient: One clodronate 800 mg tablet contains 800 mg disodium clodronate.

Inactive Ingredients: Clodronate 800 mg tablets: Silicified microcrystalline cellulose (consisting of microcrystalline cellulose and colloidal anhydrous silica), croscarmellose sodium, stearic acid, magnesium stearate, hypromellose, polyethylene glycol 400, titanium dioxide (E171).

Clodronate is intended for the treatment of bone diseases and for reduction of occurrence of bone metastases in primary breast cancer. Clodronate contains disodium clodronate as an active ingredient. Clodronate is chemically defined as bisphosphonate and is an analogue of the natural pyrophosphate. Clodronate has a strong affinity for mineralized tissues such as bone, where it inhibits bone resorption, which may be abnormally increased due to malignancy. Consequently, reduction in elevated serum calcium concentrations and a decrease in fracture risk have been observed in patients during clodronate

treatment. In patients with primary breast cancer clodronate treatment has been shown to reduce occurrence of bone metastases, and to be associated with reduced mortality.

Clodronate is indicated for the treatment of osteolysis and hypercalcemia due to malignancy and for reduction of occurrence of bone metastases in primary breast cancer.

Clodronate shall not be used concomitantly with other bisphosphonates or for patients with known hypersensitivity to bisphosphonates.

b. TOXICOLOGY

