5.5	Patients must have a Zubrod performance status of 0 - 2 (see Section 10.5).
5.6	Patients must not be co-enrolled on protocols that have bone density as an endpoint. Patients may be registered to any other locoregional or systemic therapy breast cancer study, including cooperative group studies, as long as the protocol does not specifically exclude co-enrollment.
5.7	Patients must have a serum creatinine that is ≤ 2 times the institutional upper limit of normal and a calculated creatinine clearance of ≥ 30 ml/min within 7 days prior to enrollment. Patients with renal failure are ineligible for this study.
5.8	Patients who have previously been or are currently being treated with a bisphosphonate for bone density are eligible, as long as the bisphosphonate is discontinued at registration. No other forms of bisphosphonates, other than those prescribed in this study, may be used or planned during protocol treatment, either as an adjuvant or for the treatment of osteoporosis. (Note: This study has no placebo arm, so all patients will be receiving a bisphosphonate.)

S0307 Page 27 Revised 6/12/06 Amended 6/18/07 Amended 3/11/08

SWOG Patient	No
Patient's Initia	Is (L, F, M)
5.9	Patients must undergo a dental examination within 6 months prior to initiation of treatment per Section 7.4.
—— 5.10	A patient with skeletal pain is eligible for inclusion in the study if bone scan and/or roentgenological examination fails to disclose metastatic disease. Suspicious finding must be confirmed as benign by x-ray, MRI, or biopsy.
5.11	Patients must not have a medical history of esophageal stricture or motility disorders. Patients with a history of gastroesophageal reflux disorder (GERD) are eligible, but caution should be used when administering oral bisphosphonates.
5.12	Pregnant or nursing women may not participate due to the possibility of fetal harm or harm to nursing infants from this treatment regimen (see Section 3.0). Women of reproductive potential may not participate unless they have agreed to use an effective contraceptive method while on this trial. Women of child-bearing potential must have a pregnancy test performed within 72 hours prior to initiation of treatment (see Section 7.2).

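### On the clodronate arm, Section 8.2's restart rule has no hypersensitivity exception although 3.2a bars the drug in that case, and Section 5 lacks the matching exclusion (minor)

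*Combined protocol and SAP*

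**What the plan says.** **Toxicity management.** Section 8.2 applies to all three arms. An attributed Grade 3 or greater toxicity means a hold. If it has not resolved within 3 months, the patient comes off protocol treatment. Otherwise, "If toxicity resolves (Grade 0-1) within 3 months, the protocol treatment should be restarted". Removal then becomes mandatory only if Grade 3 or greater toxicity returns. Section 8 has one removal rule tied to a particular toxicity, in 8.3: a Grade 3 or higher creatinine elevation "attributed to the bisphosphonate by the treating physician will require removal of the patient from protocol treatment". The removal criterion in 7.12b reads "Unacceptable toxicity (see Section 8.0)" and so leads back to Section 8.

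**Drug information.** Section 3.2a states: "Clodronate shall not be used concomitantly with other bisphosphonates or for patients with known hypersensitivity to bisphosphonates". It sets no grade threshold and refers to bisphosphonates as a class. Section 3.1d reports rare allergic reactions and very rare anaphylaxis with zoledronic acid, but states no bar. Section 3.3, on ibandronate, has no equivalent sentence.

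**Entry.** Section 5.8 says: "Patients who have previously been or are currently being treated with a bisphosphonate for bone density are eligible", provided that the drug is stopped at registration. Section 7.2 adds: "Patients will be randomized to zoledronic acid (Arm 1) or to clodronate (Arm 2) or to ibandronate (Arm 3)". Neither 5.1 to 5.16 nor the Fast Fact Sheet mentions hypersensitivity or allergy.

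**The concern.** A site handling a severe reaction will normally look to Section 8. It finds a general instruction to restart after recovery, one named exception (creatinine), and no pointer to Section 3. If the physician has concluded that the reaction was hypersensitivity, restarting daily clodronate is what 3.2a forbids. At that point hypersensitivity to a bisphosphonate is known.

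The same gap exists at entry. A woman who reacted to a bisphosphonate given earlier for bone density could meet every Section 5 criterion and be assigned the one study drug that the protocol bars for her. Section 5 does carry over other Section 3 warnings. Section 5.12, for example, cites Section 3.0: "Pregnant or nursing women may not participate due to the possibility of fetal harm or harm to nursing infants from this treatment regimen".

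What is at stake is the safety of individual patients. No endpoint or analysis is involved.

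**Working it through.** The sections can be compared case by case. The only arithmetic is the date on which dosing ended.

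**Case 1: attributed Grade 3 or greater hypersensitivity on clodronate, resolved to Grade 0-1 within 3 months.**
- 8.2: hold, then restart.
- 8.3: does not apply (creatinine only).
- 7.12b: returns the reader to Section 8.
- 3.2a: clodronate not to be used.
- Result: the toxicity section and the drug section disagree.

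**Case 2: attributed Grade 1 or 2 reaction on clodronate, judged to be hypersensitivity.**
- 8.2: not triggered, so Section 8 requires neither hold nor removal.
- 3.2a: still bars the drug, because it has no grade threshold.
- Result: an exception limited to Grade 3 or greater would not fully reconcile the two sections on this arm.

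**Case 3: the same reactions on zoledronic acid or ibandronate.**
- 8.2: for Grade 3 or greater, hold and then restart.
- 3.1 and 3.3: no stated bar.
- Result: no internal conflict. An exception here would be a precaution.

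**Case 4: hypersensitivity already known at entry.**
- 5.8: earlier bisphosphonate exposure allowed.
- 5.1 to 5.16: no exclusion applies.
- Prestudy Form: records the route and stop date of the earlier bisphosphonate, but has no allergy field.
- 7.2: clodronate may be assigned.
- 3.2a: clodronate not to be used.
- Result: eligibility and drug information disagree.

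**Has dosing ended?**
- Last registration: 1 February 2010 (permanent closure notice).
- Treatment starts within five working days of registration (13.1, Appendix 19.1): by about 8 February 2010.
- Oral treatment lasts 35 months (7.3, 8.4): about 8 February 2010 + 35 months = about 8 January 2013.
- Last zoledronic acid dose no later than 36 months after registration (8.4): about 1 February 2013.
- The current page of Section 8 carries a revision date of 3/28/14, after all scheduled dosing.

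**The case against.** The strongest reply is that there is no true contradiction. Section 3.2a uses mandatory wording and is specific; 8.2 says only that treatment *should* restart and is general. On a careful reading the specific bar controls. The protocol also keeps other drug-specific stop instructions in Section 3: 3.3b tells ibandronate patients to stop for symptoms of esophageal irritation, and Section 8 does not repeat that.

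There are also ways to stop. Section 8.4 allows a hold of up to 3 months for any reason, 7.12c removes a patient whose delay exceeds 3 months, and 7.12e lets her withdraw. Section 8.6 offers advice ("For treatment or dose modification related questions, please contact" is followed by named contacts), and the Off Treatment Notice has a box for a medically required stop because of toxicity.

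Most of this stands, and it is why the point is minor. But these provisions permit a stop; none makes hypersensitivity an exception to the restart rule. The reply also leaves the entry gap open.

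A reader might infer from 3.2b that severe hypersensitivity has occurred on clodronate. The text does not show that: it describes individual cases of breathing impairment resembling hypersensitivity or in aspirin-sensitive asthma, and skin reactions, all without grades. Nor do the Grade 3 and 4 tallies in the memorandum on the AZURE results (17 Grade 4 and a further 7% Grade 3 among 5,498 assessed) size the problem. They are pooled over arms, not split by attribution, and mainly musculoskeletal pain.

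**Conclusion.** The inconsistency is real and confined to the clodronate arm. Section 8.2's restart rule lacks the exception that 3.2a requires, and Section 5 lacks the matching exclusion.

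The number of women affected is unknown and probably very small. The clodronate target was 2,000 (11.2), but the documents give no hypersensitivity rate and report no restart after such a reaction. A reader might infer that the protocol directed sites to rechallenge hypersensitive women, or that women were harmed. The documents support neither, since 3.2a forbids such use and no case is described. Nor do they state a bar on zoledronic acid or ibandronate.

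The conclusion assumes that the opening lines of Section 7.0 and the consent form, which are not in the reviewed text, give no allergy instruction. Because scheduled dosing is over, changing the text can no longer alter treatment. The priority is minor.

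**What to change.** 1. **Section 8.2, with a cross-reference in 7.12b.** State that a patient judged to have a hypersensitivity reaction to her study bisphosphonate is removed from protocol treatment and not restarted. On clodronate this should apply at any grade, to match 3.2a. On zoledronic acid and ibandronate it should apply at Grade 3 or greater, as a precaution that Section 3 does not require.
2. **Section 5.** Add known hypersensitivity to bisphosphonates as an exclusion.
3. **Data check.** This is the only action left with practical effect: look for clodronate restarts after a reaction judged to be hypersensitivity. The visible preprinted terms on the Adverse Event Summary Form include rash but no allergy term, so the search should also cover the write-in lines and the expedited reports. The Treatment Summary Form gives treatment dates and dose modifications.

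The cost is one sentence, one cross-reference, one exclusion and one query. Had the change been in force during dosing, a few women would have stopped study drug earlier.
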